#### **4.1.6. Unsolicited Safety Set**

All subjects who received at least 1 dose of the study treatment (Exposed Set) that report unsolicited AEs/report not having unsolicited AEs.

#### **4.1.7. Overall Safety Set**

All subjects that belong to the Unsolicited safety or/and to the Solicited safety set.

### **4.2. Criteria for eliminating data from Analysis Sets**

Elimination codes are used to identify subjects to be eliminated from analysis. Detail is provided below for each set.

#### 4.2.1. Elimination from Exposed Set (ES)

Code 1030 (Study vaccine not administered at all), 800 (Fraudulent data) and code 900 (invalid informed consent or fraudulent data) will be used for identifying subjects eliminated from ES

#### 4.2.2. Elimination from Per protocol Set (PPS)

##### 4.2.2.1. Excluded subjects

A subject will be excluded from the PPS analysis under the following conditions

**Table 4 Elimination code and condition to exclude a subject from the PPS analysis**

Code	Condition under which the code is used	Visit (timepoints) where the code is applicable	Applicable for analysis set
800	Fraudulent data	All	All
900	Invalid informed consent	All	All
1030	Study vaccine not administered at all	All	All
1050	Randomization failure	Visit 1, 3, 5	All
1060	Randomization code was broken	All	All
1070.1	Subjects got vaccinated with the correct vaccine but containing a lower volume	Visit 1, 3, 5	All
1070.2	Vaccination not according to protocol	Visit 1, 3, 5	All
1080	Vaccine temperature deviation	Visit 1, 3, 5	All
1090	Expired vaccine administered	Visit 1, 3, 5	All
1500.1	Other deviation from study procedures not able to classified under any other categories	All	All
1500.2	Any other GCP non-compliance not able to classified under any other categories	All	All
2010	Protocol violation (inclusion/exclusion criteria)	All	All
2040	Administration of any medication forbidden by the protocol	Visit 1, 3, 5	All
2050	Not withdrawn after developing withdrawal criteria other than prohibited concomitant vaccination/medication (medical condition forbidden)	All	All
2060	Concomitant infection related to the vaccine which may influence immune response (only meningococcal infection)	All	All
2080	Subjects did not comply with vaccination schedule	Visit 3, 5	All

Code	Condition under which the code is used	Visit (timepoints) where the code is applicable	Applicable for analysis set
2090	Subjects did not comply with blood sample schedule	Visit 2, 4, 6	All
2100	Serological results not available post-vaccination for all tests	Visit 2, 4, 6	All
2120	Obvious incoherence or abnormality or error in data related to testing	Visit 2, 4, 6	All
2130	Biological sample specimen procedures not compliant with protocol	Visit 2, 4, 6	All

#### 4.2.3. Elimination from unsolicited and solicited safety set

##### 4.2.3.1. Excluded subjects

###### 4.2.3.1.1. Unsolicited safety set

Code 1030 (Study vaccine not administered at all), code 800 (fraudulent data) and code 900 (invalid informed consent) and code 1150 (no post-vaccination safety data) will be used for identifying subjects eliminated from the unsolicited safety set.

###### 4.2.3.1.2. Solicited safety set

Code 1030 (Study vaccine not administered at all), code 800 (fraudulent data) and code 900 (invalid informed consent) and code 1160 (no post-vaccination solicited safety data) will be used for identifying subjects eliminated from the solicited safety set.

## 5. STATISTICAL ANALYSES

Standard data derivation rules and statistical methods are described in section 10.1 while the study specific data derivation rules and stat methods are described in section 9.

### 5.1. Disposition of subjects

#### 5.1.1. Analysis of disposition of subjects planned in the protocol

Number of subjects enrolled, vaccinated subjects (at least 1 vaccination, full vaccination course), reason for early withdrawal, FAS, and PPS will be described by vaccine group.

#### 5.1.2. Additional considerations

Not applicable

## **5.2. Demography and baseline characteristics analyses**

### **5.2.1. Analysis of demography and baseline characteristics planned in the protocol**

Descriptive statistics (mean, standard deviation, median, minimum and maximum) for age, height, weight, and body mass index (BMI) at enrolment will be calculated overall and by vaccine group.

Distributions of subjects by sex, race, ethnic origin will be summarised overall and by vaccine group.

### **5.2.2. Additional considerations**

A summary table of important protocol deviations related to COVID-19 will be provided. Also, a listing will be produced.

## **5.3. Primary effectiveness and immunogenicity**

### **5.3.1. Analysis of primary effectiveness and immunogenicity planned in the protocol**

Refer to Glossary of terms for definitions of test-based and responder-based vaccine effectiveness. If the co-primary effectiveness objectives for rMenB+OMV NZ are met (Sections 5.3.1.1 through 5.3.1.6), then all objectives for MenACWY will be evaluated at 95% CI (Sections 5.3.1.7 through 5.3.1.11, ref Protocol Section 10.1).

#### **5.3.1.1. Vaccine effectiveness (Test-based): rMenB+OMV NZ - 3 doses (0,2,6-months schedule)**

Analysis set: Per-protocol set (PPS) will be the primary analysis population

Statistical method: The VE is defined as  $1 - RR = (1 - \text{percentage of samples without bactericidal serum activity at 1:4 dilution in MenB group} / \text{percentage of samples without bactericidal serum activity at 1:4 dilution in the ACWY group}) \times 100\%$  and it will be analyzed using a generalised linear model with vaccine group, strain, and randomization factors (i.e. region (US/ex-US), age category (10-17 YoA/18-25 YoA), previous MenACWY vaccination (y/n)) as independent variables. Furthermore, a repeated statement will be used to estimate the variance of the RR including correlation within subject's responses to different strains. If the statistical model does not converge due to (one of) the factor(s), a model without this/these factor(s) will be fitted instead. The response variable of the model will be the Bernoulli distributed outcome without bactericidal activity at a 1:4 dilution (i.e. response is 1 if titre  $< 4$ , and 0 if titre  $\geq 4$ ), at 1 month after the last vaccination (Month 7) in the MenB group and at Month 1 for the ACWY group. Each subject will contribute with approximately 35 measures to this analysis, each of the measures corresponding to the response variable to one of the 35 strains randomly assigned to be tested with the samples available for that specific subject.

In order to obtain the VE measure which is a measure based on the relative risk (RR), a generalised linear model will be used with the Binary distribution and link function log in order to compute the log RR and the corresponding 97.5% CI. The obtained values will be exponentiated to obtain the RR and the corresponding 97.5% CI. The VE will be computed as  $100\% \times (1 - RR)$ . Effectiveness of rMenB+OMV NZ (0,2,6-months schedule) will be demonstrated if the lower limit of the two-sided 97.5% CI for VE between MenB and the ACWY group is above 65%.

**5.3.1.2. Effectiveness (Responder-based): rMenB+OMV NZ - 3 doses (0,2,6-months schedule)**

Analysis set: FAS will be the primary analysis population.

Statistical method: The percentage of responders (see definition in Glossary of terms) and the corresponding exact two-sided 97.5% CI based on Clopper-Pearson method will be calculated [Clopper, 1934].

The objective is to demonstrate that the lower limit of the 97.5% CI for the percentage of responders is higher than 65%.

**5.3.1.3. Vaccine effectiveness (Test-based): rMenB+OMV NZ - 2 doses (0,6-months schedule)**

See Section 5.3.1.1

**5.3.1.4. Effectiveness (Responder-based): rMenB+OMV NZ - 2 doses (0,6-months schedule)**

See Section 5.3.1.2

**5.3.1.5. Vaccine effectiveness (Test-based): rMenB+OMV NZ - 2 doses (0,2-months schedule)**

See Section 5.3.1.1

**5.3.1.6. Effectiveness (Responder-based): rMenB+OMV NZ - 2 doses (0,2-months schedule)**

See Section 5.3.1.2

**5.3.1.7. Lot-to-lot consistency: MenABCWY - ACWY component**

Analysis set: The analysis of lot-to-lot consistency will be based on the PPS.

Statistical method: For each of the three ABCWY lots (Lots 1, 2 and 3 of the MenACWY component of the ABCWY vaccine), GMTs and 97.5% CIs will be calculated by exponentiating (base 10) the least squares means and the lower and upper limits of the 97.5% CIs of the log transformed titres (base10) obtained from an Analysis of Variance

(ANOVA) with factors for vaccine lot and randomization factors (i.e. region (US/ex-US), age category (10-17 YoA/18-25 YoA), previous MenACWY vaccination (y/n)).

Additionally, lot-to-lot GMT ratios will be computed for each pair of ABCWY lots.

Ninety-seven point five percent (97.5%) CIs for the ratios of GMTs will be constructed by exponentiating the difference of the least square means of the log transformed titres and the lower and upper limits of the 97.5% CIs on the difference obtained from the ANOVA model above.

**Lot-to-lot consistency criterion:** The three ABCWY lots will be considered equivalent if for each of the 4 serogroups A, C, W and Y and each pair of vaccine lots, the two-sided 97.5% CI on the ratio of GMTs at 1 month after the last vaccination will be contained within the interval [0.5, 2.0].

If the co-primary effectiveness objectives for rMenB+OMV NZ are met (Sections 5.3.1.1 through 5.3.1.6), then the above will be evaluated at 95% CI.

#### **5.3.1.8. Immunological non-inferiority: MenABCWY vs. MenACWY**

**Analysis set:** PPS restricted to subjects without previous ACWY vaccination will be the primary analysis population.

**Statistical method:** The percentage of subjects with 4-fold rise\*P in hSBA titres against MenACWY indicator strains A, C, W and Y and the corresponding exact two-sided 97.5% CIs based on Clopper-Pearson method will be calculated for the ABCWY (pooled lots) group and the ACWY group [Clopper, 1934]. The 97.5% CIs for the difference in percentages between ABCWY (pooled lots) and ACWY group will be constructed using the method of Miettinen and Nurminen [Miettinen, 1985].

**Non-Inferiority criterion:** Non-inferiority of MenABCWY vaccine for the proportion of subjects with 4-fold rise will be demonstrated if the lower limit of the two-sided 97.5% CI for the difference in percentage of subjects with 4-fold rise between the 2 groups (ABCWY (pooled) lots –ACWY) is above -10%.

\* For the Men A, C, W, Y evaluation, the 4-fold rise is defined as:

- a post-vaccination hSBA titre  $\geq 4$  times the LOD for subjects with a pre-vaccination hSBA titre  $< \text{LOD}$
- a post-vaccination hSBA titre  $\geq 4$  times the LLOQ for subjects with a pre-vaccination hSBA titre  $\geq \text{LOD}$  but  $< \text{LLOQ}$ , and
- a post-vaccination hSBA titre  $\geq 4$  times the pre-vaccination titre for subjects with a pre-vaccination hSBA titre  $\geq \text{LLOQ}$ .

Table 5 reads the LOD and LLOQ of MenACWY indicator strains used in the definition of 4-fold rise provided by the laboratory.

**Table 5 LOD and LLOQ of MenACWY indicator strains**

Strain	LOD	LLOQ
Men A (3125)	CCI	
Men C (C11)		
Men W (240070)		
Men Y (860800)		

If the co-primary effectiveness objectives for rMenB+OMV NZ are met (Sections 5.3.1.1 through 5.3.1.6), then the above will be evaluated at 95% CI.

#### **5.3.1.9. Vaccine effectiveness (Test-based): MenABCWY**

See Section 5.3.1.1. If the co-primary effectiveness objectives for rMenB+OMV NZ are met (Sections 5.3.1.1 through 5.3.1.6), then the VE for MenABCWY will be evaluated at 95% CI.

#### **5.3.1.10. Effectiveness non-inferiority: MenABCWY vs. rMenB+OMV NZ**

Analysis set: PPS will be the primary analysis population.

Statistical method: The percentage of samples with bactericidal activity measured by enc-hSBA at 1:4 dilution and the corresponding exact two-sided 97.5% CIs based on Clopper-Pearson method will be calculated for the ABCWY (pooled lots) group and the MenB group comparator that will be selected (ref: the footnote of Figure 2). The 97.5% CIs for the difference in percentages between ABCWY (pooled lots) and selected MenB group will be constructed using the method of Miettinen and Nurminen [Miettinen, 1985].

Non-Inferiority criterion: Non-inferiority of MenABCWY vaccine for the percentage of samples with bactericidal activity measured by enc-hSBA at 1:4 dilution will be demonstrated if the lower limit of the two-sided 97.5% CI for the difference between the 2 groups (ABCWY (pooled) lots – MenB) is above -5%.

If the co-primary effectiveness objectives for rMenB+OMV NZ are met (Sections 5.3.1.1 through 5.3.1.6), then the above will be evaluated at 95% CI.

#### **5.3.1.11. Effectiveness (Responder-based): MenABCWY**

See Section 5.3.1.2. If the co-primary effectiveness objectives for rMenB+OMV NZ are met (Sections 5.3.1.1 through 5.3.1.6), then the effectiveness (responder-based) for MenABCWY will be evaluated at 95% CI.

### 5.3.2. Additional considerations

Analyses of the primary effectiveness and immunogenicity objectives will be repeated by age group (10-17 years of age and 18-25 years of age), race, sex, region (US/ ex-US), and subjects with and without a previous MenACWY vaccination (primed and unprimed).

#### 5.3.2.1. Vaccine effectiveness (Test-based): rMenB+OMV NZ - 3 doses (0,2,6-months schedule)

The SAS code to analyse the Vaccine effectiveness (Test-based): rMenB+OMV NZ - 3 doses (0,2,6-months schedule) objective is specified below. Treatment, region, age category, previous ACWY vaccination, and strains will be modelled as fixed effect. To account for a possible over-dispersion, the DSCALE option in the model statement will be evaluated first. The DSCALE will be kept in the model only if the F-statistics for the DSCALE parameter is significant ( $p<0.05$ ). The following SAS code will be used for the VE calculation:

```

ods trace on;
ods output GEEmpPEst = genmod_stats
CONVERGENCESTATUS = converge ;

PROC GENMOD data=dataset descending;
class trtgrp strain region agecat previousACWY subject_id ;
model outcome = trtgrp strain region agecat previousACWY / dist= bin
link= log DSCALE;
repeated subject = subject_id / type= CS withinsubject= strain;
estimate 'MenB026-ACWY' trtgrp 1 0 0 0 0 -1/ alpha=0.025 exp;

/*trtgrp R is MenB0,2,6 and trtgrp W is ACWY*/

run;

ods output close;

data genmod_stats;
set genmod_stats;
where parm = 'trtgrp' and level1 = '1';
rr = exp(estimate);
ub = exp(uppercl);
ve = (1 - rr)*100 ;
ve_ll = (1 - ub) * 100 ;
if ve_ll > 65 then success = 1 ;
else success = 0 ;
run;

```

where outcome represents the Bernoulli distributed outcome without bactericidal activity at a 1:4 dilution (i.e. response is 1 if titre  $< 4$ , and 0 if titre  $\geq 4$ ), one month after the 3rd vaccination in MenB 0,2,6 and one month after the MenACWY vaccination for the ACWY arm, trtgrp indicates the vaccine groups, strain is the serogroup B strain variable, region is either US or ex-US, agecat is the age at enrolment (10-17 YoA or 18-25 YoA), and previousACWY is previous ACWY vaccination (y/n) at enrolment.

rr is the relative risk (RR), which is obtained from the estimated parameters from PROC GENMOD. Vaccine effectiveness (VE) is then derived as (1-rr)x100%.

ub represents the upper bound of the 97.5% CI of the relative risk. ve\_ll is the lower bound of the 97.5% CI for VE, if the value is greater than 65%, then the Vaccine effectiveness (Test-based): rMenB+OMV NZ - 3 doses (0,2,6-months schedule) objective is successful.

#### **5.3.2.2. Effectiveness (Responder-based): rMenB+OMV NZ - 3 doses (0,2,6-months schedule)**

Not applicable

#### **5.3.2.3. Vaccine effectiveness (Test-based): rMenB+OMV NZ - 2 doses (0,6-months schedule)**

See Section 5.3.2.1, with the difference in the treatment arm:

```
PROC GENMOD data=dataset descending;
class trtgrp strain region agecat previousACWY subject_id ;
model outcome = trtgrp strain region agecat previousACWY / dist= bin
link= log DSCALE ;
repeated subject = subject_id / type= CS withinsubject= strain ;
estimate 'MenB06-ACWY' trtgrp 0 1 0 0 -1/ alpha=0.025 exp;
/*trtgrp S is MenB0,6 and trtgrp W is ACWY*/
run;
```

#### **5.3.2.4. Effectiveness (Responder-based): rMenB+OMV NZ - 2 doses (0,6-months schedule)**

Not applicable

#### **5.3.2.5. Vaccine effectiveness (Test-based): rMenB+OMV NZ - 2 doses (0,2-months schedule)**

See Section 5.3.2.1, with the difference the outcome data for group R is from one month after the 2nd vaccination instead of one month after the 3rd vaccination.

#### **5.3.2.6. Effectiveness (Responder-based): rMenB+OMV NZ - 2 doses (0,2-months schedule)**

Not applicable

#### **5.3.2.7. Lot-to-lot consistency: MenABCWY - ACWY component**

Not applicable

### 5.3.2.8. Immunological non-inferiority: MenABCWY vs. MenACWY

As a sensitivity analysis, a parametric model will be run. A generalized linear model with factors for vaccine group and randomization factors (i.e. region (US/ex-US), age category (10-17 YoA/18-25 YoA)) will be ran, with the Binary distribution and link function is identity, and outcome is 4-fold rise. If the lower limit of the two-sided 97.5% CI for the difference in percentage of subjects with 4-fold rise between the 2 groups (ABCWY (pooled) lots –ACWY) coming from the model is above -10%, also the sensitivity analysis has demonstrated non-inferiority. If the co-primary effectiveness objectives for rMenB+OMV NZ are met (Sections 5.3.1.1 through 5.3.1.6), then the above will be evaluated at 95% CI.

### 5.3.2.9. Vaccine effectiveness (Test-based): MenABCWY

See Section 5.3.2.1, with the difference in the estimate statement:

```
PROC GENMOD data=dataset descending;
class trtgrp strain region agecat previousACWY subject_id ;
model outcome = trtgrp strain region agecat previousACWY / dist= bin
link= log DSCALE ;
repeated subject = subject_id / type= CS withinsubject= strain ;
estimate 'MenABCWY-ACWY' trtgrp 0 0 1 1 1 -3/ alpha=0.025 exp
divisor=3;

/*trtgrp T, U, and V are the ABCWY-1, ABCWY-2, and ABCWY-3 lots and
trtgrp W is ACWY*/
run;
```

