
Vaccine effectiveness (Test-based): MenABCWY vaccine
 
To demonstrate the effectiveness of the MenABCWY vaccine against a randomly selected panel of endemic US N. meningitidis serogroup B invasive disease strains as measured by enc-hSBA at 1 month after the last MenABCWY vaccination (0,6-months) when compared to 1 month after the MenACWY vaccination.
 
Criterion:
 
LL of the two-sided 97.5% CI^ for vaccine effectiveness is above 65% against a randomly selected strain panel between the ABCWY group (pooled lots) and the ACWY group.
	
The percentages of samples without bactericidal serum activity using enc-hSBA against each of the endemic US N. meningitidis serogroup B strains, at 1 month after the:
 
 
last vaccination for the ABCWY group (pooled) (Day 211, Month 7), and
 
1 month after the MenACWY vaccination in the ACWY group (Day 31, Month 1).
 

Effectiveness non-inferiority: MenABCWY vaccine vs. rMenB+OMV NZ vaccine
 
To demonstrate the non-inferiority of the effectiveness of the MenABCWY vaccine (0,6-months schedule) compared to the rMenB+OMV NZ vaccine (0,2,6-months or 0,6-months or 0,2-months)† in terms of percentage of samples with bactericidal serum activity using enc-hSBA against a randomly selected panel of endemic US N. meningitidis serogroup B invasive disease strains.
	
The percentages of samples with bactericidal serum activity using enc-hSBA against each of the endemic US N. meningitidis serogroup B strains at 1 month after the:
 
 
last MenABCWY vaccination (Day 211, Month 7) for the ABCWY group (pooled lots), and
 
3-dose vaccination series of rMenB+OMV vaccine (Day 211, Month 7 in MenB_0_2_6 group) or 2-dose vaccination series (Day 211, Month 7 in MenB_0_6 group) or 2-dose vaccination series (Day 91, Month 3 in MenB_0_2_6 group)†
 

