\* MenB\_0\_2\_6 group will also be evaluated for objectives pertaining to 0,2-months vaccination schedule.

Note 1: A MenB lot will be used for the pre-filled syringe component of the MenACWY vaccine.

Note 2: The groups ABCWY-1, ABCWY-2, ABCWY-3 will be pooled into a single group, ABCWY (pooled lots) (except for analysis of lot to lot consistency).

\*\* Note 3: In order to let the subjects in MenB\_0\_2\_6 group receive a dose of MenACWY vaccine and for subjects in ACWY group to receive the second dose of rMenB+OMV NZ in line with the vaccine as standard of care (also in line with the Advisory Committee on Immunization Practices (ACIP) recommendations in the US [ACIP, 2011]), the subjects in these groups will receive a vaccination of MenACWY and rMenB+OMV NZ vaccines, respectively, on Day 211 (Visit 6) after completion of the post-vaccination 3 blood sampling. To maintain the blinding of the study, subjects in the rest of the groups (MenB\_0\_6, ABCWY-1, ABCWY-2 and ABCWY-3) will receive a dose of Placebo. All these vaccines/ product administered at Day 211 are not associated with any study objectives/ endpoints (Safety assessment

conducted after 1 dose of rMenB+OMV NZ in the ACWY group at Day 181 is to maintain the blind of the study).

- Duration of the study: The study duration is approximately 18 months for each subject.
- Primary completion Date (PCD): T10; Day 541.

Refer to [Glossary of terms](#) for the definition of PCD.

- End of Study (EoS): the date of release of the last testing results, to be achieved not later than 8 months after Last Subject Last Visit (LSLV) (LSLV = T10; Day 541). If the completion of testing occurs prior the completion of the LSLV the latter date defines the end of study visit.

Refer to [Glossary of terms](#) for the definition of EoS.

- Study groups:

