### 5.3.2.9. Vaccine effectiveness (Test-based): MenABCWY

See Section 5.3.2.1, with the difference in the estimate statement:

```
PROC GENMOD data=dataset descending;
class trtgrp strain region agecat previousACWY subject_id ;
model outcome = trtgrp strain region agecat previousACWY / dist= bin
link= log DSCALE ;
repeated subject = subject_id / type= CS withinsubject= strain ;
estimate 'MenABCWY-ACWY' trtgrp 0 0 1 1 1 -3/ alpha=0.025 exp
divisor=3;

/*trtgrp T, U, and V are the ABCWY-1, ABCWY-2, and ABCWY-3 lots and
trtgrp W is ACWY*/
run;
```

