\* MenB\_0\_2\_6 group will also be evaluated for objectives pertaining to 0,2-months vaccination schedule.

Note 1: A MenB lot will be used for the pre-filled syringe component of the MenACWY vaccine.

Note 2: The groups ABCWY-1, ABCWY-2, ABCWY-3 will be pooled into a single group, ABCWY (pooled lots) (except for analysis of lot to lot consistency).

\*\* Note 3: In order to let the subjects in MenB\_0\_2\_6 group receive a dose of MenACWY vaccine and for subjects in ACWY group to receive the second dose of rMenB+OMV NZ in line with the vaccine as standard of care (also in line with the Advisory Committee on Immunization Practices (ACIP) recommendations in the US [ACIP, 2011]), the subjects in these groups will receive a vaccination of MenACWY and rMenB+OMV NZ vaccines, respectively, on Day 211 (Visit 6) after completion of the post-vaccination 3 blood sampling. To maintain the blinding of the study, subjects in the rest of the groups (MenB\_0\_6, ABCWY-1, ABCWY-2 and ABCWY-3) will receive a dose of Placebo. All these vaccines/ product administered at Day 211 are not associated with any study objectives/ endpoints (Safety assessment

conducted after 1 dose of rMenB+OMV NZ in the ACWY group at Day 181 is to maintain the blind of the study).

- Duration of the study: The study duration is approximately 18 months for each subject.
- Primary completion Date (PCD): T10; Day 541.

Refer to Glossary of terms for the definition of PCD.

- End of Study (EoS): the date of release of the last testing results, to be achieved not later than 8 months after Last Subject Last Visit (LSLV) (LSLV = T10; Day 541). If the completion of testing occurs prior the completion of the LSLV the latter date defines the end of study visit.

Refer to Glossary of terms for the definition of EoS.

- Study groups:

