**5.4.1.2. Effectiveness by each of the endemic US *N. meningitidis* serogroup B strains**

Analysis set: FAS will be the primary analysis population. The ABCWY (pooled lots) group and the MenB group comparator that will be selected (ref: the footnote of Figure 2) will be used for the purpose of this analysis.

Statistical method: The VE per strain will be calculated as described in Section 5.3.1.1, using a generalised linear model with vaccine group, and randomization factors (i.e. region (US/ex-US), age category (10-17 YoA/18-25 YoA), previous MenACWY vaccination (y/n)) as independent variables, and alpha=0.05 leading to 95% CI. In case for a strain 100% response will be observed in both vaccine groups, VE against these strain will be assessed by calculating 95% CI for relative risk from raw proportions, and VE=1-RR.

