### 5.4.2.2. Effectiveness by each of the endemic US N. meningitidis serogroup B strains

The SAS code to analyse the Vaccine effectiveness (Test-based): rMenB+OMV NZ - 3 doses (0,2,6-months schedule) by strain is specified below. Treatment, and randomization factors (i.e. region (US/ex-US), age category (10-17 YoA/18-25 YoA), previous MenACWY vaccination (y/n)) will be modelled as fixed effect. To account for a possible over-dispersion, the DSCALE option in the model statement will be evaluated first. The DSCALE will be kept in the model only if the F-statistics for the DSCALE parameter is significant ( $p < 0.05$ ). The following SAS code will be used for the VE calculation:

```

ods trace on;
ods output GEEEmpPEst = genmod_stats
CONVERGENCESTATUS = converge ;

PROC GENMOD data=dataset descending;
class trtgrp region agecat previousACWY;
by strain ;
model outcome = trtgrp region agecat previousACWY / dist= bin link= log
DSCALE alpha=0.05;
estimate 'MenB026-ACWY' trtgrp 1 0 0 0 0 -1/ alpha= 0.05 exp;

/*trtgrp R is MenB0,2,6 and trtgrp W is ACWY*/

run;

ods output close;

data genmod_stats;
set genmod_stats;
by strain ;
where parm = 'trtgrp' and level1 = '1';
rr = exp(estimate);
ub = exp(uppercl);
ve = (1 - rr)*100 ;
ve_ll = (1 - ub) * 100 ;
if ve_ll > 65 then success = 1 ;
else success = 0 ;
run;

```

where outcome represents the Bernoulli distributed outcome without bactericidal activity at a 1:4 dilution (i.e. response is 1 if titre < 4, and 0 if titre  $\geq$  4), one month after the 3rd vaccination in MenB0,2,6 and one month after the MenACWY vaccination for the ACWY arm, trtgrp indicates the vaccine groups, strain is the serogroup B strain variable, region is either US or ex-US, agecat is the age at enrolment (10-17 YoA or 18-25 YoA), and previousACWY is previous ACWY vaccination (y/n) at enrolment.

rr is the relative risk (RR), which is obtained from the estimated parameters from PROC GENMOD. Vaccine effectiveness (VE) is then derived as (1-rr)x100%.

ub represents the upper bound of the 95% CI of the relative risk. ve\_ll is the lower bound of the 95% CI for VE, if the value is greater than 65%, then the Vaccine effectiveness (Test-based): rMenB+OMV NZ - 3 doses (0,2,6-months schedule) objective is successful.

In summary in case of convergence issue the following hierarchical decision tree will be applied

- Binary model including region, agecat, and previousACWY
- Binary model, excluding region, agecat, and previousACWY

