- Cochran-Mantel-Haenszel (CMH) method (if strain has 100% killed or 0% killed for ANY treatment)
- VE set to 0% (if strain has 100% killed for both treatment)

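### The VE programs keep the three MenABCWY lots as separate treatment levels although the SAP pools them: little effect on the primary VE, but avoidable separation or method switching in the by-strain VE

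*SAP*

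**What the plan says.** All references are to SAP Amendment 9, the current text.

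**The rule.** Note 2 in section 3.2 states: "The groups ABCWY-1, ABCWY-2, ABCWY-3 will be pooled into a single group, ABCWY (pooled lots) (except for analysis of lot to lot consistency". The primary MenABCWY criterion in Table 1 sets the 65% limit for VE against a "randomly selected strain panel between the ABCWY group (pooled lots) and the ACWY group". For by-strain VE, section 5.4.1.2 names the analysis groups as "The ABCWY (pooled lots) group and the MenB group comparator that will be selected".

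**The all-strain code.** Section 5.3.2.9 has six treatment levels, R to W. Its comment reads "trtgrp T, U, and V are the ABCWY-1, ABCWY-2, and ABCWY-3 lots", and its contrast is "estimate 'MenABCWY-ACWY' trtgrp 0 0 1 1 1 -3/ alpha=0.025 exp", completed by a divisor of 3. Strain is a main effect, with no treatment-by-strain term.

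**The by-strain code.** Section 5.4.2.2 fits each strain separately. Its only contrast is "estimate 'MenB026-ACWY' trtgrp 1 0 0 0 0 -1/ alpha= 0.05 exp". The six coefficients show that the lots are still separate levels. No by-strain MenABCWY contrast is written.

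**The fallback.** The decision tree closing 5.4.2.2 applies when there is a convergence issue. Its third step is "Cochran-Mantel-Haenszel (CMH) method (if strain has 100% killed or 0% killed for ANY treatment". Its last step covers full killing in both treatments. The SAP does not say whether a treatment here is a lot or the pooled group.

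**The concern.** The text and the code define different quantities. On a log link, the mean of three lot log RRs is the log of the geometric mean of the lot RRs. The pooled-group RR uses the arithmetic mean of the lot failure rates (for lots of equal size). The two agree only when the lots have equal failure rates.

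The difference becomes serious when a lot has no unkilled serum. Its log RR then goes to minus infinity and takes the average with it, while the pooled group still has an ordinary RR. This can happen in a by-strain fit, where the counts per lot are small, and most readily for the strains the vaccine covers best. By-strain VE is a secondary endpoint. At stake is whether its MenABCWY estimates and confidence limits are reportable, and come from one method, for those strains.

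**Working it through.** **Inputs from the SAP.** Section 3.3 gives 912, 548 and 183 randomised (per MenB group, per lot, ACWY) and 25% dropout. The panel has 110 strains (3.1), with about 35 tested per subject (5.3.1.1).

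**Reproducing the stated figures.** 912 × 0.75 = 684; 548 × 0.75 = 411; 183 × 0.75 = 137.25, stated as 137. The total is 2 × 912 + 3 × 548 + 183 = 3651. All agree.

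**Sera per strain.** Evaluable × 35/110 gives 411 × 35/110 ≈ 131 per lot and 137 × 35/110 ≈ 44 for ACWY. By-strain VE uses the FAS, so counts may be larger. The ceiling is 548 × 35/110 ≈ 174 per lot.

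**Chance of an empty lot.** With true unkilled rate q and n sera per lot, p0 = (1 − q)^n. At least one empty lot has probability 1 − (1 − p0)³. An empty pooled group has probability p0³. The rates q are assumptions.

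| q | p0, n = 131 | At least one lot empty, n = 131 | At least one lot empty, n = 174 | Pooled group empty, n = 131 |
|---|---|---|---|---|
| 1% | 0.268 | 61% | 44% | 1.9% |
| 2% | 0.071 | 20% | 9% | 0.04% |
| 3% | 0.018 | 5.5% | 1.5% | under 0.001% |

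At q = 5% and n = 131 the chance of at least one empty lot is about 0.4%.

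**By-strain example.** Illustrative counts: 0, 2 and 3 unkilled of 131 in the three lots, and 38 of 44 in ACWY.

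- Pooled: RR = (5/393)/(38/44) = 0.0147, so VE = 98.5%. SE(log RR) = √(1/5 − 1/393 + 1/38 − 1/44) = 0.448. The upper RR limit is 0.0147 × exp(1.96 × 0.448) = 0.0355, so the 95% lower limit for VE is 96.5%.
- Lots separate, averaged contrast: a log-binomial fit without covariates gave VE 99.998% with a log-scale SE of about 3,820, so no usable lower limit. The fit still reported convergence. This was statsmodels; GENMOD's behaviour was not tested.
- With no empty lot (1, 2 and 2 unkilled) the codings agree: 98.6% separate and 98.5% pooled, lower limit 96.5% for both.

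**All-strain model, empty lot.** A simulated log-link GEE (strain main effect, robust SE, reduced to 30 strains with 10 per subject), with one lot forced to zero unkilled on one strain, gave VE 80.26% (lower limit 79.09%) with lots separate and 80.25% (79.09%) pooled. No harm arises.

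**All-strain model, unequal lots.** Assume 80% unkilled in ACWY.

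- Lots at 14/18/22%: the arithmetic mean is 18, giving VE 1 − 18/80 = 77.5%. The geometric mean is (14 × 18 × 22)^(1/3) = 17.70, giving 77.9%. The difference is 0.4 points.
- Lots at 12/18/24%: the geometric mean is 17.31, giving 78.4% against 77.5%. The difference is 0.9 points.
- Equal lots: no difference.

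**The case against.** A reader might infer that the primary program in 5.3.2.9 itself breaks down, or that an empty lot is bound to give a strain a VE near 100% with no lower limit. The SAP supports neither.

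- The 5.3.2.9 program is the all-strain model. It estimates one RR per lot across all strains, and an empty lot on one strain leaves it essentially unchanged.
- The averaged by-strain MenABCWY contrast is an inference. Section 5.4.2.2 writes only the MenB contrast, and 5.4.1.2 calls for the pooled group. The six-level coding makes carry-over the natural reading, because 5.3.2.9 holds the only MenABCWY contrast given for that coding, but it is not stated.
- The fallback may catch the case. If a treatment means a lot, an empty lot meets the CMH condition and the runaway estimate need not appear. The two bad outcomes are alternatives and do not occur together.
- An upward bias in the primary VE needs lots that differ. They differ in the ACWY component (3.1), while the outcome is killing of serogroup B strains. Nothing in the SAP suggests unequal failure rates. With equal planned lot sizes, an equal-weight contrast is a recognised way to combine them.
- The by-strain objective carries no success criterion in Table 1.

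These points limit the size and certainty of the problem. They do not remove the contradiction between rule and code, and the fallback is not a reliable safeguard. It starts only on a convergence issue, which a separated fit may not report. If a treatment means the pooled group, an empty lot does not meet its condition. If it means a lot, a strain with an estimable pooled RR changes method for no reason, and read literally one empty lot could move the MenB comparisons for that strain too.

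**Conclusion.** The concern holds in a limited form. The VE programs do not implement the pooled ABCWY group that Note 2, the primary criterion and 5.4.1.2 require.

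For the primary MenABCWY VE the effect is nil with equal lots and under 1 point at the assumed spreads, so the conclusion against 65% is unlikely to change. For by-strain VE, a lot with no unkilled serum separates the fit. If the averaged contrast is carried over, the result has one of two forms:

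- VE near 100% with no usable lower limit, when no convergence problem is flagged or treatment means the pooled group.
- A needless move to CMH, when the fallback starts and treatment means a lot.

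The frequency rests on assumed unkilled rates of 1% to 3% and on 131 to 174 sera per lot per strain: roughly 61–44%, 20–9% and 5.5–1.5% of strains at those rates. At 5% it is rare. The change is worth making because it gives the estimand the SAP already names and avoids a problem that falls mainly on well-covered strains.

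**What to change.** 1. Recode ABCWY-1, -2 and -3 to one level in every VE model (5.3.2.1, 5.3.2.3, 5.3.2.5, 5.3.2.9 and 5.4.2.2), leaving four levels in the order MenB_0_2_6, MenB_0_6, ABCWY, ACWY.
2. Write the contrasts as `1 0 0 -1`, `0 1 0 -1` and `0 0 1 -1`, with no divisor, and write out the MenABCWY contrast in the by-strain code of 5.4.2.2.
3. In the 5.4.2.2 decision tree, trigger the fallback on a zero or full cell in either of the two groups being compared, in place of any treatment or a reported convergence issue.
4. Keep lot levels only for lot-to-lot consistency (5.3.1.7).

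The cost is SAP and program wording. No new data or subjects are needed.
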